3.2 DISCUSSION OF TRIAL DESIGN, INCLUDING THE CHOICE OF CONTROL GROUP

According to current guidelines (ADA, EASD), insulin therapy should be initiated immediately in patients newly diagnosed with T2DM with an HbA_{1c} >8.5% and as a second step in patients with insufficient glycaemic control despite treatment with oral antidiabetic agents [R10-5741]. Therefore, patients with current insulin therapy alone or combined with metformin represent an important proportion of the patient population with T2DM.

Due to its mechanism of action and the low risk for hypoglycaemia induction, DPP-4 inhibitors like linagliptin should provide additional efficacy in combination with the planned background therapy, especially in postprandial glucose control. The patients enter the study on the basis of insufficient glycaemic control despite standard treatment with insulin alone or combined with metformin. The placebo-controlled design is considered ethically acceptable on the basis of appropriate criteria for patient discontinuation and criteria for rescue therapy as defined in the relevant guidelines (e.g. FDA Guidance for Industry for developing drugs in diabetes [R08-2669]).

The study duration with stable background therapy is planned for 24 weeks because HbA_{1c} as the primary endpoint has been demonstrated to be a reflection of the glycaemic control over the preceding 12 weeks and a stable effect could be shown at 24 weeks [P13-12370]. The one week follow-up period is considered to be sufficient, as previous studies with linagliptin have shown that the pharmacodynamic effect of linagliptin only extends to about 7 days after the last dose.

3.3 SELECTION OF TRIAL POPULATION

Up to 400 patients will be screened for the trial in 20-30 investigational sites in China to ensure that 206 Chinese patients are randomised to trial treatment (103 to each treatment group) and complete the trial.

It is planned to have at least 90 randomised patients on both background of pre-mixed insulin and basal insulin, which will be handled through IRT and refer to [section 7.6](#).

If the patient's background type distribution is not balanced as expected, the impact on the study conduct should be carefully considered. The sponsor should further monitor the recruitment of the trial with regard to the type of patient's background treatment. The intent is to obtain a balanced mix of patients pre-treated with premixed insulin or basal insulin. As such the sponsor may cap specific patient populations.

It is expected that at least 5 patients should be randomised at each trial centre. Investigators who fail to screen at least one patient within the first 6 weeks of the site initiation may be excluded from further participation. If enrolment is delayed, additional centres may be recruited.

Permission to randomise more than 20 patients per site must be obtained from the Trial Clinical Monitor at Boehringer Ingelheim.

Screening of patients for this trial is competitive, i.e. screening for the trial will stop at all centres when such a number of patients has been screened that it is anticipated that a sufficient number of patients will be randomised to trial treatment. Investigators will be notified when the appropriate number of patients has been screened and screening is complete, and will not be allowed to recruit additional patients for this study. Patients who have completed Visit 1 procedures prior to notification of the termination of recruitment will be allowed to continue in the study, if they meet all entry criteria and they are able to follow the visit schedule specified in this protocol.

The check for patient eligibility will be based upon a complete medical history including a physical examination and clinical laboratory tests. Judgement of the clinical relevance of a concomitant disease is at the discretion of the investigator. Conditions under therapy are always clinically relevant.

A log of all patients enrolled into the trial (i.e. who have signed informed consent) will be maintained in the ISF at the investigational site irrespective of whether they have been treated with investigational drug or not.

3.3.1 Main diagnosis for trial entry

The study will be performed in Chinese patients with T2DM who have insufficient glycaemic control despite diet and exercise and receiving insulin alone or in combination with metformin.

3.3.2 Inclusion criteria

1. Diagnosis of type 2 diabetes mellitus prior to informed consent.
2. Chinese male or female patients who are pre-treated with insulin alone or in combination with metformin:
 - With maximum insulin dose of ≤ 1 unit/kg/day. Acceptable basal insulins could be insulin glargin, insulin detemir or NPH (neutral protamin hagedorn) insulin with duration of action up to 24 h; acceptable pre-mixed insulins could be preparations with 25/75 or 30/70 ratio, with once or twice daily posology only. The total insulin dose should not be changed by more than 10% of the baseline value within the 12 weeks prior to randomisation (Visit 3). Both human insulin & insulin analogue are accepted.
 - If the patient is taking metformin, stable dose (at least 1500 mg daily) must be maintained for at least 12 weeks without dose adjustments prior to randomisation (Visit 3).
3. HbA_{1c} fulfills the following criteria: ≥ 7.5 % to ≤ 10.0 % at Visit 1.

4. Age \geq 18 years at Visit 1.
5. BMI \leq 45 kg/m² (Body Mass Index) at Visit 1.
6. Women of childbearing potential must be ready and able to use highly effective methods of birth control per ICH M3 (R2) that result in a low failure rate of less than 1% per year when used consistently and correctly. A list of contraception methods meeting these criteria is provided in the patient information.
 - A woman is considered of childbearing potential (WOCBP), i.e. fertile, following menarche and until becoming post-menopausal unless permanently sterile.
 - Permanent sterilisation methods include hysterectomy, bilateral salpingectomy and bilateral oophorectomy.
7. Signed and dated written informed consent by date of Visit 1 in accordance with ICH-GCP and local legislation

3.3.3 Exclusion criteria

1. Uncontrolled hyperglycaemia with a glucose level >240 mg/dl (>13.3 mmol/L) after an overnight fast during placebo run-in and confirmed by a second measurement (not on the same day).
2. Any other antidiabetic drug within 3 months prior to informed consent except those defined as background treatment via inclusion criterion 2.
3. Acute coronary syndrome (non-STEMI, STEMI and unstable angina pectoris), stroke or TIA within 3 months prior to informed consent.
4. Indication of liver disease, defined by serum levels of either ALT (SGPT), AST (SGOT), or alkaline phosphatase above $3 \times$ upper limit of normal (ULN) as determined during screening and/or run-in phase.
5. Any contraindications to metformin according to the local label for those patients that enter the study with metformin therapy as provided in ISF.
6. Bariatric surgery within the past two years and other gastrointestinal surgeries that induce chronic malabsorption.
7. Medical history of cancer (except for basal cell carcinoma) and/or treatment for cancer within the last 5 years.
8. Blood dyscrasias or any disorders causing hemolysis or unstable Red Blood Cell (e.g. malaria, babesiosis, haemolytic anemia).
9. Known hypersensitivity or allergy to the investigational product or its recipients.
10. Treatment with anti-obesity drugs 3 months prior to informed consent or any other treatment at the time of screening (i.e. surgery, aggressive diet regimen, etc.) leading to unstable body weight.
11. Current treatment with systemic steroids at time of informed consent or change in dosage of thyroid hormones within 6 weeks prior to informed consent or any other uncontrolled endocrine disorder except T2DM.
12. Women who are pregnant, nursing, or who plan to become pregnant while in the trial.

13. Alcohol or drug abuse within the 3 months prior to informed consent that would interfere with trial participation or any ongoing condition leading to a decreased compliance to study procedures or study drug intake in the opinion of the investigator.
14. Participation in another trial with an investigational drug within 2 months prior to informed consent or previous enrolment in this trial.
15. Any other clinical condition that would jeopardize patient's safety while participating in this clinical trial in the opinion of the investigator.

3.3.4 Removal of patients from therapy or assessments

3.3.4.1 Removal of individual patients

An excessive withdrawal rate can have a severe negative impact on the scientific value of the trial. Every effort should be made to keep patients in the trial as scheduled. This includes careful patient selection and appropriate explanation of the trial requirements and procedures prior to enrolment as well as an explanation of the consequences of premature withdrawal.

An individual patient is to be withdrawn from trial treatment if:

- The patient withdraws consent for trial treatment or trial participation, without the need to justify the decision.
- The patient needs to take concomitant drugs that interfere with the investigational product or other study medications.
- The patient can no longer be treated with trial medication for other medical reasons (such as surgery, adverse events, other diseases, or pregnancy).
- Introduction of rescue therapy due to hyperglycaemia as described in [section 4.2.1](#) does not lead to sufficient treatment efficacy (rescue criteria still met). In this case, the reason for discontinuation will be classified as "lack of efficacy".
- Occurrence of hypoglycaemia that may put the patient at risk with continued participation (e.g. repeated hypoglycaemic episodes).
- If a patient becomes pregnant during the trial the investigational drug will be stopped, the patient will be discontinued from the trial and the patient will be followed up until birth or otherwise termination of the pregnancy.
- The patient has repeatedly shown to be non-compliant with important trial procedures and, in the opinion of both, the investigator and sponsor representative, is not willing or able to stick to the trial requirements in the future.

Given the patient's agreement, the patient will undergo the procedures for early treatment discontinuation and follow up as outlined in the [Flow Chart](#) (FC) and [section 6.2.3](#).

For all patients the reason for withdrawal (e.g. adverse events) must be recorded in the CRF (case report form). These data will be included in the trial database and reported.

A patient can be discontinued after discussion between sponsor and investigator if eligibility criteria are being violated, or if the patient fails to comply with the protocol (e.g. non-attendance at study assessments).

Patients who drop out during the screening phase prior to randomisation (Visit 3) will be considered a screening failure. They have to be recorded as screening failure in eCRFs and no further follow-up is required.

Patients who discontinue or withdraw from the study after randomisation (Visit 3) will be considered as “early discontinuations” and the reason for premature discontinuation must be recorded in the eCRFs. The data will be included in the trial database and will be reported. If determined by investigator as necessary for patient safety, new antidiabetic medication regimen can be started immediately after discontinuation and must be recorded in eCRFs.

Patients who withdraw or discontinue from the trial after randomisation will not be replaced.

3.3.4.2 Discontinuation of the trial by the sponsor

Boehringer Ingelheim reserves the right to discontinue the trial overall or at a particular trial site at any time for the following reasons:

1. Failure to meet expected enrolment goals overall or at a particular trial site
2. Emergence of any efficacy/safety information invalidating the earlier positive benefit-risk-assessment that could significantly affect the continuation of the trial
3. Violation of GCP, the Clinical Trial Protocol (CTP), or the contract disturbing the appropriate conduct of the trial

The Investigator / the trial site will be reimbursed for reasonable expenses incurred in case of trial termination (except in case of the third reason).

4. TREATMENTS

4.1 INVESTIGATIONAL TREATMENTS

The study medication will be provided by Boehringer Ingelheim Pharma GmbH & Co. KG.

4.1.1 Identity of the Investigational Medicinal Products

The characteristics of the test product are below.

- Substance: linagliptin
- Pharmaceutical form: tablet
- Source: Boehringer Ingelheim Pharma GmbH & Co. KG
- Unit Strength: 5 mg
- Route of administration: p.o., once daily

The characteristics of the reference product are below.

- Substance: placebo matching linagliptin 5 mg
- Pharmaceutical form: tablet
- Source: Boehringer Ingelheim Pharma GmbH & Co. KG
- Unit Strength: NA
- Route of administration: p.o., once daily

4.1.2 Selection of doses in the trial

The doses of 5 mg linagliptin was selected based on the results from previous dose finding studies (please refer to the actual version of the Investigator's Brochure, [[c01838725-16](#)]) and represents the final to be marketed dose for linagliptin.

4.1.3 Method of assigning patients to treatment groups

When a patient is qualified for entry into the randomised double-blind treatment period, treatment assignment will be by means of a third-party phone/web-based randomisation at Visit 3. This will involve the use of interactive response technology (IRT). To facilitate the use of the IRT, the Investigator will receive an IRT manual including all necessary instructions for using the IRT. A copy of the manual will be available in the ISF.

Patients will be randomly assigned to linagliptin film-coated tablet 5 mg or placebo for linagliptin film-coated tablet 5 mg in a 1:1 ratio. The randomisation will be stratified by HbA_{1c} (< 8.5% vs. ≥ 8.5%) as determined from the blood sample taken at Visit 1 and insulin type (basal insulin vs pre-mixed insulin). For further details please refer to [Section 7.6](#).

Patient assignment to the treatment groups will be determined by a computer generated random sequence. Access to the randomisation code will be controlled and documented – for

further details please refer to Sections 4.1.5.1 and [4.1.5.2](#).

The assigned medication number will be entered in the eCRF, and the corresponding medication kit should be given to the patient. Using this procedure, relevant parties will be blinded to the treatment group assignment.

4.1.4 Drug assignment and administration of doses for each patient

Patients who qualify will be randomised to linagliptin 5 mg or placebo. Medication will be dispensed in a double-blind manner.

Patients will be assigned a placebo run-in kit at the beginning of the placebo run-in period (Visit 2), and dispensing will occur just once. Dispensing of kits for the double-blind treatment period will begin at Visit 3. Dispensing will occur on 5 occasions over a period of 24 weeks. For further details regarding packaging (e.g. number of tablets per pack) please refer to [Section 4.1.6](#).

From the start of the placebo run-in period (Visit 2), patients should be instructed to take their trial medication once daily with water. To ensure a dose interval of about 24 hours, the medication should be taken at the same time every day. If a dose is missed by more than 12 hours, that dose should be skipped and the next dose should be taken as scheduled. No double doses should be taken, and dose reductions are not permitted. Linagliptin can be taken with or without food.

Patients should be instructed not to take their trial medication on the morning of study visits as they will be dosed whilst in the trial site. Patients who fail to do so should have the visit rescheduled as soon as possible, ideally on the following day. Visits should be routinely scheduled in the morning, at approximately the same time of day (07:00 AM to 11:00 AM) for each visit. The actual date and time of administration of the medication at the trial visit will be recorded in the eCRF.

Patients will continue with their standard insulin with or without concomitant metformin therapy throughout the entire study.

4.1.5 Blinding and procedures for unblinding

4.1.5.1 Blinding

Patients, Investigators and everyone involved in trial conduct or analysis or with any other interest in this double-blind trial will remain blinded with regard to the randomised treatment assignments until after database lock.

The randomisation code will be kept secret by Clinical Trial Support at BI up to database lock. Please refer to Section 4.1.5.2 for the rules regarding breaking the code for an individual or for all patients in emergency situations.

4.1.5.2 Unblinding and breaking the code

Emergency unblinding will be available to the Investigator / Pharmacist / investigational drug storage manager via IRT. It must only be used in an emergency situation when the identity of the trial drug must be known to the Investigator in order to provide appropriate medical treatment or otherwise assure safety of trial participants. The reason for unblinding must be documented in the source documents and/or appropriate CRF page along with the date and the initials of the person who broke the code.

Due to the requirements to report Suspected Unexpected Serious Adverse Reactions (SUSARs), it may be necessary for a representative from Boehringer Ingelheim's Pharmacovigilance group to access the randomisation code for individual patients during trial conduct. The access to the code will only be given to authorised Pharmacovigilance representatives and not be shared further.

4.1.6 Packaging, labelling, and re-supply

The investigational products will be provided by BI or a designated CRO. They will be packaged and labelled in accordance with the principles of Good Manufacturing Practice (GMP).

The study medication will consist of packs labelled with the trial identification and medication kit number. Each pack will contain an appropriate number of linagliptin tablets or matching linagliptin placebo with some reserve (see below), for dosing until the next scheduled visit.

The placebo run-in kit, assigned to all patients successfully completing Visit 2, will contain 21 tablets (i.e. sufficient supply for 2 weeks, with 1 week in reserve). Each double-blind treatment period kit will contain 42 tablets (i.e. sufficient supply for 4 weeks, with 2 weeks in reserve). At Visit 3, 4 and 5, the patient will receive 1 treatment kit. At Visit 6 and 7, the patient will receive 2 treatment kits.

Re-supply to the sites will be managed via an IRT system, which will also monitor expiry dates of supplies available at the sites

For details of packaging and the description of the label, refer to the ISF.

4.1.7 Storage conditions

Drug supplies will be kept in their original packaging and in a secure limited access storage area according to the recommended storage conditions on the medication label. A temperature log must be maintained for documentation.

The minimum/maximum storage temperature must be measured and documented by the Investigator / pharmacist / investigational drug storage manager in accordance with BI (or designated CRO) SOPs.

4.1.8 Drug accountability

The Investigator / pharmacist / investigational drug storage manager will receive the investigational drugs delivered by the Sponsor when the following requirements are fulfilled:

- approval of the study protocol by the Institutional Review Board (IRB) / ethics committee
- availability of a signed and dated clinical trial contract between the sponsor and the head of the investigational site
- approval / notification of the regulatory authority, e.g. competent authority
- availability of the curriculum vitae of the Principal Investigator
- availability of a signed and dated clinical trial protocol
- if applicable, availability of the proof of a medical licence for the Principal Investigator

The Investigator < and/or > Pharmacist < and/or > investigational drug storage manager must maintain records of the product's delivery to the trial site, the inventory at the site, the use by each patient, and the return to the sponsor or warehouse / drug distribution centre or alternative disposal of unused products. If applicable, the sponsor or warehouse / drug distribution centre will maintain records of the disposal.

These records will include dates, quantities, batch/serial numbers, expiry ('use by') dates, and the unique code numbers assigned to the investigational product and trial patients. The Investigator / pharmacist / investigational drug storage manager will maintain records that document adequately that the patients were provided the doses specified by the CTP and reconcile all investigational products received from the Sponsor. At the time of return to the Sponsor / appointed CRO, the Investigator / pharmacist / investigational drug storage manager must verify that all unused or partially used drug supplies have been returned by the clinical trial patient and that no remaining supplies are in the Investigator's possession.

4.2 OTHER TREATMENTS, EMERGENCY PROCEDURES, RESTRICTIONS

4.2.1 Other treatments and emergency procedures

Throughout the duration of the trial, patients should continue to take insulin alone or in combination with metformin as background therapy.

Acceptable basal insulins could be insulin glargin, insulin detemir or NPH (neutral protamin hagedorn) insulin with duration of action up to 24 h; acceptable pre-mixed insulins could be preparations with 25/75 or 30/70 ratio, with once or twice daily posology only. The background medication of metformin should remain unchanged throughout the study. The total prescribed insulin dose should not be changed by more than 10% of the baseline value in the 24 weeks after randomisation. The background medication will not be provided as part of the clinical trial supplies.

The patients can take their background medication as they are used to, where it is suggested that basal insulin is always given in the evening. Morning dose of metformin/any permitted pre-mixed insulin and study medication should be taken after the visits blood sample taken, and the patients should have the same habits of dosing throughout the trial.

Hyperglycaemia

If the following FPG criteria are met and if further supported by HBGM results during the same time period, investigators may increase or adjust the patient's permitted antidiabetic therapy (i.e., the patient's background therapy of stable insulin prior to or after informed consent, and if applicable metformin) for the treatment of hyperglycaemia [[R08-2669](#)]:

Week	Visit	FPG level
Week 1-12	up to visit 6	>240 mg/dl (>13.3 mmol/l) after overnight fast
Week 12-24	after visit 6 until Visit 8	>200 mg/dl (>11.1 mmol/l) after overnight fast

To confirm the above results, meaning that there is a minimum of two measurements, at least one of which should be performed after an overnight fast at the investigational site, and on a different day to the initial measurement.

If the above criteria are met, the investigator should increase or adjust (e.g., by changing the timing of administration, etc.) the patient's permitted antidiabetic therapy to improve glycaemic control according to investigator's discretion and the changes should be documented in the eCRF.

The first choice of rescue therapy should be the adjustment of insulin therapy. Its dosage will be left to the discretion of the investigator. In very rare cases, adjustment of background therapy or addition of another oral anti-diabetic medication would be appropriate. Such cases should be discussed with the local clinical monitor or the Trial Clinical Monitor (TCM). Rescue therapy should be taken in accordance with the local prescribing information of the respective drug, taking into account potential contraindications.

The following permitted antidiabetic therapy will be considered to be rescue therapy:

- **For patients with a baseline daily insulin dose ≤ 10 units, any increase of insulin >50% from baseline for > 7 days duration**
- **For patients with a baseline daily insulin dose >10 and ≤ 20 units, any increase of insulin >30% from baseline for > 7 days duration**
- **For patients with a baseline daily insulin dose > 20 units, any increase of insulin >20% from baseline for > 7 days duration**
- **Any increase in metformin for ≥ 1 day**
- **Any introduction of a new antidiabetic therapy for ≥ 1 day.**

A FPG, HbA_{1c} sample should be taken before initiation of rescue therapy and sent to central lab for analysis. The HbA_{1c} sample is not required if a sample has been taken and sent to the central lab for analysis within the last 4 weeks.

Hypoglycaemia

If the patient is experiencing hypoglycaemia (criteria see [section 5.3.7](#)), the investigator should review the diary responses to diet and physical activity as well as the HBGM results to determine the appropriate approach to reduce occurrences of hypoglycaemia (e.g., encouraging the patient not to skip meals, increasing carbohydrate intake if increasing exercise, decreasing or adjusting the patient's permitted antidiabetic therapy).

In the case of hypoglycaemia that may put patient on risk (e.g. repeated symptomatic hypoglycaemia or severe hypoglycaemia), appropriate adjustment of anti-diabetic therapy such as a dose reduction / discontinuation of ongoing rescue medication or existing background therapy should be initiated. Reduction or discontinuation of ongoing rescue medication should be considered before a reduction in the dose of existing background therapy.

If, in the Investigator's clinical opinion, no further effect from the rescue medication is anticipated, and the patient's hyper- or hypoglycaemia cannot be controlled, the patient should be discontinued from the trial as specified in [Section 3.3.4](#).

Any rescue medication will be recorded in the source documents and on the appropriate pages of the eCRF.

Rescue medication will not be provided as part of the clinical trial supplies.

Any additional treatment, that does not qualify as a rescue medication, and is considered necessary for the patient's welfare may be given at the discretion of the Investigator. Exceptions to this are the restrictions described in Section 4.2.2.

In this trial, the background therapy (i.e. insulin alone or in the combination with metformin) and the chosen rescue medications are considered as Auxiliary Medicinal Product (AMP). This means that in the event of SAEs, the Investigator will assess the causal relationship of the SAE to the AMPs. Further details regarding SAE reporting can be found in [Section 5.3.6](#).

There are no special emergency procedures to be followed.

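### Do the statements on changing background insulin in Protocol 4.2.1, and the silence of SAP violation code D1.2, leave the analysis unsettled?

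*Protocol*

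**What the plan says.** Protocol 4.2.1 makes five statements that bear on insulin changes after randomisation.

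- A general limit: "The total prescribed insulin dose should not be changed by more than 10% of the baseline value in the 24 weeks after randomisation".
- Under its own Hyperglycaemia subheading, once the fasting plasma glucose (FPG) criteria are confirmed: "If the above criteria are met, the investigator should increase or adjust" the permitted antidiabetic therapy, at the investigator's discretion.
- On rescue: "The first choice of rescue therapy should be the adjustment of insulin therapy", with the dosage left to the investigator.
- Two sentences later: "In very rare cases, adjustment of background therapy or addition of another oral anti-diabetic medication would be appropriate". Such cases are to be discussed with a monitor.
- Further on, a description of "the background therapy (i.e. insulin alone or in the combination with metformin".

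An insulin increase counts as rescue only above a tier set by the baseline dose. For baselines above 20 units the tier is "any increase of insulin >20% from baseline for > 7 days duration". The tiers for smaller doses are 30% and 50%, with the same duration.

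SAP Table 6.2:1 has code D1.2, an efficacy-type violation. It applies when an antidiabetic drug outside the protocol's rescue definition is taken although the FPG criterion of code D1.1 is not met. It does not mention insulin dose changes.

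**The concern.** Three things look unsettled. First, the 10% sentence carries no exception, yet the same section tells investigators to go beyond it when FPG is high. Second, insulin is part of the background therapy, so read literally the same insulin increase is both the first choice of rescue and a very rare case needing discussion with a monitor. Third, an increase above 10% that stays within the rescue tier is neither inside the limit nor rescue. The protocol allows "Any additional treatment, that does not qualify as a rescue medication" at the investigator's discretion, while D1.2 might be read as making such an increase a violation.

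If so, sites could follow different instructions from one section, and two people classifying the same patient could disagree. Efficacy-type violations remove a patient from the per-protocol set (SAP 6.2) and are tabulated (SAP 7).

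**Working it through.** **Size of the zone between the limit and rescue.** Inputs are the 10% limit and the three tiers in Protocol 4.2.1. The lower bound is 0.10 × baseline dose and the upper bound is tier × baseline dose, in whole units.

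| Baseline (units) | 10% limit | Rescue only above | Increases in between |
|---|---|---|---|
| 10 | 0.10 × 10 = 1 | 0.50 × 10 = 5 | 2 to 5 |
| 20 | 0.10 × 20 = 2 | 0.30 × 20 = 6 | 3 to 6 |
| 30 | 0.10 × 30 = 3 | 0.20 × 30 = 6 | 4 to 6 |
| 40 | 0.10 × 40 = 4 | 0.20 × 40 = 8 | 5 to 8 |

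Larger increases lasting 7 days or less also fall in this zone.

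**When D1.2 could arise.** D1.1 uses FPG below 90% of the rescue threshold with no documented hyperglycaemia. The SAP's own figure reproduces: 0.9 × 240 = 216 mg/dL. For the later threshold, 0.9 × 200 = 180 mg/dL.

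**The 10% sentence beside the rest of the protocol.** Protocol 2.3 lets investigators modify insulin at any time for safety. It also says that patients who exceed the hyperglycaemia limits of 4.2.1 get rescue or have their background therapy adjusted. Protocol 3.1 asks for unchanged background therapy only as far as possible. The hypoglycaemia text in 4.2.1 allows reductions. So the limit is the default, and the exceptions are written down, though partly in other sections.

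**D1.2 beside the rest of the SAP.** D1.2 sits under the heading for prohibited medication. Background insulin is required by inclusion criterion 2, so it is not prohibited. The criterion is about a drug being taken and contains no dose limit. If background insulin were such a drug, D1.2 would flag every patient on an unchanged dose who never met the FPG criterion, which cannot be meant. It has other targets, such as the herbal antidiabetic preparations barred in Protocol 4.2.2.1. The SAP history table also shows that a separate category for background therapy not taken as specified was deleted in the final version of 26 September 2017.

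**Effect on the primary analysis.** It uses the full analysis set and sets values after rescue to missing (Protocol 7.3.1, SAP 6.6 and 7.4.1). The tiers define which insulin increases are rescue. Neither the 10% sentence nor D1.2 enters that rule. The sample size does not depend on them either: with 100 per group, a difference of 0.55 and SD 1.1, a two-sample t-test gives 94.0% power, against the stated 94%.

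**The case for a change.** The strongest point is the pair of rescue sentences. Both places in 4.2.1 that describe background therapy include insulin, so "The first choice of rescue therapy should be the adjustment of insulin therapy" and "In very rare cases, adjustment of background therapy or addition of another oral anti-diabetic medication would be appropriate" cannot both hold as written. The second may have been meant for metformin only, but the text does not say so, and a site cannot tell which adjustments need the monitor. This stands. The passages must be reconciled, and the content is for the sponsor's clinicians.

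A second point is that insulin changes can influence the estimate, because values after increases that are not rescue stay in the analysis. That is also true. As an illustration on assumptions not found in the documents, suppose an extra 5% to 30% of placebo patients had such increases, each lowering HbA1c by a further 0.2 to 0.4 points. The difference would fall from 0.55 to between 0.55 − 0.05 × 0.2 = 0.54 and 0.55 − 0.30 × 0.4 = 0.43, and power from 94% to between 93% and 79%. But this follows from where the rescue tiers were set. Extending D1.2 to these patients would leave every one of those values in the primary analysis.

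A third point is that the deleted category does not by itself say what D1.2 covers. On its own it would not settle the matter. Together with the heading and the wording of the criterion, it does. For any hard case, Protocol 7.5 already requires evaluability of patients with confounding deviations to be decided before unblinding.

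**Conclusion.** No change to the statistical plan follows. The 10% limit is a default with exceptions given in Protocol 2.3, 3.1 and 4.2.1. On a sensible reading, D1.2 does not reach dose changes in background insulin. What remains is a drafting slip in the rescue paragraph of 4.2.1, which the sponsor must reconcile as an editorial matter. It affects instructions to sites, not the analysis.

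The full analysis set, the model, the handling of values after rescue and the sample size are the same however the wording is settled. At most, the count of important violations and membership of the per-protocol set could shift, by a number the documents do not give. The published SAP Table 6.3:1 assigns no analysis to that set.

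This rests on two assumptions. The SAP takes its rescue definition from its Section 5.3, which is not in the published text and is assumed to match the protocol's tiers. Any per-protocol analysis in unpublished text is assumed to be supportive only, since both documents place the primary analysis on the full analysis set.
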